#### 10.2.1.5 Clinical Global Impression-Severity of Illness (CGI-S)

The CGI-S is administered by an experienced neurologist familiar with MSA patients to make an expert clinical global judgement about the severity of the disease across various time points. The neurologist makes a judgement about the total picture of the patient at each visit: the disease severity, the patient's level of distress and other aspects of impairment, and the impact of disease on functioning. The rating is based upon observed and reported symptoms, behaviour, and function at the time of assessment. The CGI-S is rated on a scale ranging from 0 to 4 (whereas the 0 = normal, not impaired; 1 = mildly impaired; 2 = moderately impaired; 3 = severely impaired; 4 = extremely impaired).

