24.1.5 Clinical Global Impression Severity Scale (CGI-S)

The CGI-S is administered by an experienced neurologist familiar with MSA patients to make an expert clinical global judgement about the severity of the disease across various time points. The neurologist makes a judgement about the total picture of the patient at each visit: the disease severity, the patient's level of distress and other aspects of impairment, and the impact of disease on functioning. The rating is based upon observed and reported symptoms, behaviour, and function in the past seven days. Symptoms and behaviour may fluctuate over a week; the score should therefore reflect the average severity level across the seven days. The CGI-S is rated on a scale ranging from 0 to 4 (whereas the 0 = normal, not impaired; 1 =mildly impaired; 2 = moderately impaired; 3 = severely impaired; 4 = extremely impaired).

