24.1.6 Patient global Impression Scale (PGI-S)

The PGI-S is a self-reported single item to evaluate all aspects of patients' MSA symptoms. Patients are asked to choose the response that best describes the severity of their MSA symptoms over the past week. The question is rated on a 5-point scale ranging from 0 to 4 (0 = none; 1 = minor; 2 = moderate; 3 = severe; 4 = very severe). It takes approximately 1 minute to complete the PGI-S.

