Records to be used in descriptive statistics or statistical analyses will be flagged with ANL01FL=Y and ANL02FL=Y. ANL01FL = Y and ANL02FL=Y will be assigned to all valid assessments (NOMWEEK not equal to 888) unless an assessment at the Withdrawal Visit or an Unscheduled Visit is assigned to the same analysis week as a scheduled visit (having the same NOMWEEK). In this case, ANL01FL = Y will be assigned to one valid visit prioritized in the following order: Scheduled Visit, Unscheduled Visit, and Withdrawal Visit.

CGI-S, PGI-S, and OGI-S will follow the same windowing principles since these were administered at the exact same visits as the UMSARS. The remaining COAs, i.e., SE-ADL, COMPASS Select Change and EQ-5L-5D were only administered at Week 24, 48 and 72 (Visit 12, 18, and 24) post-baseline in the DBP, and hence the broad windowing will only contain these visits using the above intervals, meaning that some observations might be deemed invalid for this mapping. However, they will be mapped into the above narrow windows as well using the continuous windowing approach. The same principles will be applied for the OLEP.

Remission in the CGI-S, PGI-S or OGI-S score (defined as a score of 1 or 2) at each analysis week following a baseline will be included as new parameters (PARAM=*Remission*).

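### SAP 24.2.1 defines remission on CGI-S, PGI-S and OGI-S as a score of 1 or 2, but on these 0-4 scales 0 is the best level and 2 is moderate

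*SAP*

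**What the plan says.** After describing the visit windows for the global impression scales, SAP section 24.2.1 adds a new analysis parameter: "Remission in the CGI-S, PGI-S or OGI-S score (defined as a score of 1 or 2) at each analysis week following a baseline". The operative words are "defined as a score of 1 or 2". It is to be stored in the analysis data under its own parameter name.

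The scales are described elsewhere in the SAP and in the protocol, and the two documents agree on range and anchors:

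- **CGI-S** (SAP 24.1.5; Protocol 10.2.1.5). The SAP says "The CGI-S is rated on a scale ranging from 0 to 4". The protocol's anchors are "0 = normal, not impaired; 1 = mildly impaired; 2 = moderately impaired; 3 = severely impaired; 4 = extremely impaired".
- **PGI-S** (SAP 24.1.6; Protocol 10.2.1.6). The anchors are "0 = none; 1 = minor; 2 = moderate; 3 = severe; 4 = very severe".
- **OGI-S** (SAP 24.1.7; Protocol 10.2.1.7). The range and anchors are the same as for PGI-S.

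SAP Panel 7, which sets worst-rank values after death, assigns 4 to each of the three scales. That fits a scale whose worst level is 4.

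**The concern.** On a severity scale where lower is better, a remission category should contain the best level. This one leaves it out and includes the middle level instead. The rule is therefore not ordered with severity: moving from 1 to 0 loses remission, and worsening from 0 to 1 gains it.

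The stake is modest but real. The SAP commits to deriving the parameter, and a programmer will implement the definition as written. SAP chapter 6 presents categorical variables by default as counts and, where relevant, percentages. Any such table would carry the authority of a prespecified definition while giving remission counts that do not mean what the label says.

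**Working it through.** No sample size, power or error-rate figure is involved, and the plan states no remission rate to reproduce. The check is to apply the rule to every level of each scale.

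**Inputs**

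- Rule: remission if the score is 1 or 2 (SAP 24.2.1).
- Levels and anchors: 0 to 4 (SAP 24.1.5 to 24.1.7; Protocol 10.2.1.5 to 10.2.1.7).

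**Rule applied to each level**

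| Score | CGI-S | PGI-S and OGI-S | Coded as remission? |
|---|---|---|---|
| 0 | normal | none | No |
| 1 | mild | minor | Yes |
| 2 | moderate | moderate | Yes |
| 3 | severe | severe | No |
| 4 | extreme | very severe | No |

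**Rule applied to short score sequences at successive post-baseline assessments**

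- 2, 1, 0 (steady improvement): yes, yes, no.
- 0, 1, 2 (steady worsening): no, yes, yes.
- 2, 2, 2 (no change): yes, yes, yes.

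The first two sequences show that the coding runs against the direction of the scale at its lower end. The third shows that a patient can be in remission throughout without any improvement.

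**Could the documents resolve it elsewhere?** Neither document recodes these scales to start at 1 or gives another definition of remission. The sentence is current SAP text and no redaction touches it.

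**Where would the parameter be used?**

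- Remission is not among the endpoints in SAP section 4.
- SAP Panel 2 lists CGI-S, PGI-S and OGI-S as continuous secondary variables. SAP 14.4.2 analyses such variables by MMRM on change from baseline.
- The covariate analysis in SAP 14.3.7 uses the baseline CGI-S category, not remission.
- For the open-label extension, SAP 14.6 plans descriptive summaries and an MMRM of continuous endpoints.

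No planned model takes the parameter as input.

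**The case against.** The strongest reply is that nothing depends on the parameter. It appears once, in a data-handling section, and no listed endpoint, test or model uses it. That stands, and it limits the point to a correction of the dataset specification. It does not make the rule right. The SAP still commits to producing the parameter, and its own default for categorical variables is to count them.

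A second reply is that where remission ends is a judgement. This stands in part. Including level 2 is hard to defend against an anchor of moderate impairment, but it turns on what the sponsor means by remission. Excluding level 0 does not: no cut-off on a severity scale can include 1 and leave out the level better than it.

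A reader might also infer more than the text allows:

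- **That many patients would be in remission at baseline.** The parameter is derived only for weeks after a baseline, and neither document gives a baseline distribution on these scales. What can be said is that a patient who stays at 1 or 2 is coded as remitted at each assessed week after baseline.
- **That remission is coded at every visit.** In the double-blind period the scales are scheduled at Weeks 12, 24, 36, 48, 60 and 72, plus converted end-of-treatment or withdrawal visits. In the extension, CGI-S and PGI-S are scheduled only at selected visits, and OGI-S is not listed.
- **That exactly two of the five levels are misclassified.** This presumes that the correct rule is 0 or 1. If remission meant 0 alone, three levels (0, 1 and 2) would be wrong. The documents supply no reference definition.
- **That the rule was carried over from a scale starting at 1.** This is plausible, since 1 and 2 would be the two best levels there, but neither document mentions such a scale.

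**Conclusion.** The definition is wrong as written and the point is minor. On all three scales it excludes the best level, includes the moderate level and codes an improvement from 1 to 0 as a loss of remission. This rests only on the anchors in the two documents and on the ordinary reading that remission cannot exclude the least severe state.

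Its effect is limited to the derived parameter and to any counts or percentages made from it. The primary and key secondary analyses and the MMRM analyses of CGI-S, PGI-S and OGI-S do not change. The number of patients affected cannot be calculated without score distributions, which the documents do not give.

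**What to change.** Before unblinding, do one of two things in SAP 24.2.1:

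1. Delete the remission parameter. This is the simpler course, since no listed endpoint uses it.
2. Keep it, but reconcile its definition with the 0-4 anchors so that it includes 0. The sponsor should choose the upper cut-off and give a reason for it, as the documents supply none. The SAP should also say where the parameter will be reported.

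The cost is one line in the SAP and the matching line in the dataset specification. No data collection, endpoint or model changes.

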24.2.2 MRI parameters

MRI parameters (volumetric, DTI and ASL) are assessed at the following visits, and hence a broad windowing will only be applied for these visits. A narrow window will also be defined using all per-protocol defined efficacy visits as scheduled in Panel 16 above. Only MRI volumetric will be evaluated in the OLEP.

Nominal Vis Number (DB-Period)	Nominal Vis Week	Nominal Vis Day	Time Window narrow ¹	Time Window broad ¹
V3 (Baseline Visit)	0	0	-7 to 7	-7 to 7
V9 (planned MRI Visit)	12	84	70 to 98	15 to 126
V12 (planned MRI Visit)	24	168	155 to 182	127 to 210
V18 (planned MRI Visit)	48	336	323 to 350	295 to 378
V24 (planned UMSARS/EoTDBP Visit)	72	504	491 to 518	463 to 518
Nominal Visit Number (OLE-Period)				
V1E (baseline OLEP Visit) ²	0E	0	-7 to 7	-7 to 7
V13E (planned EoTOLE Visit)	48E	336	323 to 350	295 to 350

Panel 17 Visit Windows for MRI

All post-baseline visits (except EoT visits) can be converted into a Withdrawal (WD) Visit. ¹ For DBP and OLEP, respectively, the applied narrow window will be continuous (i.e., ± 14 days) to avoid invalid assessments (protocol text ± 3 days). The broad window is set up as continuous as well to match. ² EoTDBP Visit will work as Baseline Visit for the OLEP if done within the acceptable window.

24.2.3 Blood sampling parameters

For blood sampling for IMP, safety lab (only one performed also at screening), α -synuclein and ADA the following windowing will be applied with the addition of the Visit 6 and the Safety follow-up Visit (SFU).

Nominal Vis Number (DB-Period)	Nominal Vis Week	Nominal Vis Day	Time Window narrow ¹	Time Window broad ¹
V1 (Screening Visit – planned sampling)	-6	-42	NA	NA
V3 (Baseline Visit – planned sampling)	0	0	-7 to 7	-7 to 7
V5 (planned sampling Visit)	4	28	21 to 35	21 to 35
V6 (planned sampling Visit)	6	42	36 to 49	36 to 49
V7 (planned sampling Visit)	8	56	50 to 69	50 to 69
V9 (planned sampling Visit)	12	84	70 to 98	70 to 126
V10 (WD Visit)	16	112	99 to 126	NA
V11 (WD Visit)	20	140	127 to 154	NA
V12 (planned sampling Visit)	24	168	155 to 182	127 to 210
V13 (WD Visit)	28	196	183 to 210	NA
V14 (WD Visit)	32	224	211 to 238	NA
V15 (planned sampling Visit)	36	252	239 to 266	211 to 294
V16 (WD Visit)	40	280	267 to 294	NA
V17 (WD Visit)	44	308	295 to 322	NA
V18 (planned sampling Visit)	48	336	323 to 350	295 to 378
V19 (EoTDBP/WD Visit)	52	364	351 to 378	NA
V20 (EoTDBP/WD Visit)	56	392	379 to 406	NA
V21 (planned sampling Visit)	60	420	407 to 434	379 to 462
V22 (EoTDBP/WD Visit)	64	448	435 to 462	NA
V23 (EoTDBP/WD Visit)	68	476	463 to 490	NA
V24 (planned sampling EoTDBP/WD Visit)	72	504	491 to 518	463 to 518
V25 (planned sampling SFU Visit)	88	616	609 to 623	595 to 630

Panel 18 Visit Windows for Blood Sampling Parameters

Nominal Visit Number (OLE-Period)	Nominal Visit Number (OLF-Period)					
$\frac{1}{2} = \frac{1}{2} = \frac{1}$	0E	0	7 +- 7	7 4 - 7		
VIE (BL OLEP VISIT – planned sampling)	UE	0	-/ 10 /	-/ 10 /		
V2E (WD Visit)	4E	28	15 to 42	NA		
V3E (WD Visit)	8E	56	43 to 69	NA		
V4E (WD Visit)	12E	84	70 to 98	NA		
V5E (WD Visit)	16E	112	99 to 126	NA		
V6E (WD Visit)	20E	140	127 to 154	NA		
V7E (planned sampling Visit)	24E	168	155 to 182	127 to 210		
V8E (WD Visit)	28E	196	183 to 210	NA		
V9E (WD Visit)	32E	224	211 to 238	NA		
V10E (WD Visit)	36E	252	239 to 266	NA		
V11E (WD Visit)	40E	280	267 to 294	NA		
V12E (WD Visit)	44E	308	295 to 322	NA		
V13E (EoTOLE Visit – planned sampling)	48E	336	323 to 350	295 to 350		
SFU-E (planned sampling SFU Visit	64E	448	434 to 462	434 to 462		

All post-baseline visits (except EoT visits) can be converted into a Withdrawal (WD) Visit. ¹ For DBP and OLEP, respectively, the applied narrow window will be continuous (i.e., ± 14 days) to avoid invalid assessments (protocol text ± 3 days). The broad window is set up to allow additional flexibility. ² EoTDBP Visit will work as Baseline Visit for the OLEP if done within the acceptable window.

Since CSF sampling for IMP, NfL, t-tau and α -synuclein quantification only is planned for Visit 3 (Baseline), Visit 18 and Visit 72, the above broad windowing will only be applied around these visits. The above narrow windowing will be identical. CSF sampling will not be performed in the OLEP.

Blood sampling for NfL will be assessed at Screening Visit and Baseline Visit Pre-IMP and at Visit 9, 12, 15, 18, 24, 1E, 7E and 13E post-IMP, and hence the above broad windowing will only be applied around these visits. Again, the above narrow windowing will be fully applied in addition.

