CSF sampling o			$\sqrt{}$															$\sqrt{}$						√p	
Other Study Procedures as	nd A	Asse	ssm	ents	5																				
IMP administration r			√		√		1		1	1		1	1	1	1	√	√	√	√	1	√	1	1		
Concomitant medication (prescription and non-prescription)	√	V	V	√	√	√	√	V	V	√	1	1	√	√	V	√	√	√	√	√	√	√	√	√	√
Pregnancy test, urine dipstick w		√	√		√		1		√	√	1	1	√	√	√	√	√	√	√	√	√	√	√	√	1
Exit interview (subset) x																								$\sqrt{}$	

ADA = anti-drug antibody; AE = adverse event; ASL = arterial spin labelling; BL = baseline; CGI-S = Clinical Global Impression – Severity of Illness; CSF = cerebrospinal fluid; C-SSRS = Columbia-Suicide Severity Rating Scale; COMPASS = Composite Autonomic System Score; DBP = Double-blind Period; DNA = deoxyribonucleic acid; DTI = diffusion-tensor imaging; ECG = electrocardiogram; EOI = end of infusion; EoT = End-of-Treatment; EoTDBP = End-of-Treatment DBP; EQ-5D-5L = EuroQol 5-Dimensions, 5-Levels; IMP = investigational medicinal product; IRT = Interactive Response Technology; MoCA = Montreal Cognitive Assessment; MRI = magnetic resonance imaging; MSA = Multiple System Atrophy; MSA-C = MSA with predominant cerebellar features; MSA-P = MSA with predominant parkinsonism; NfL = neurofilament light chain; OGI-S = Observer-rated Global Impression – Severity of Illness; OLE = Open-label Extension Period; PGI-S = Patient Global Impression – Severity of Illness; PK = pharmacokinetics; RNA = ribonucleid acid; SAE = serious adverse event; SCR = screening; SE-ADL = Schwab & England Activities of Daily Living; SFU = Safety Follow-up of DBP; T-tau = total tau; UMSARS = Unified Multiple System Atrophy Rating Scale; US = United States; vMRI = volumetric magnetic resonance imaging; WD = withdrawal

- a. When the last patient randomized reaches Visit 18/Week 48, the remaining patients in the DBP will have their next scheduled visit converted to an EoTDBP Visit (assessments as listed for Visit 24, no IMP administration).
- b. Patients who withdraw, except for those who withdraw their consent, will be asked to attend a Withdrawal Visit as soon as possible.
- c. The Safety Follow-up Visit will take place 20 weeks after last IMP administration. This will apply only to patients who do not enter the OLE or if timing of the Safety Follow-up Visit will be before their first visit in the OLE.

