1.4 Exploratory Objectives

- To explore the target engagement of Lu AF82422 to α -synuclein
- To explore the target engagement of Lu AF82422 on pathological species of α-synuclein
- To explore the relationship between UMSARS, MRI parameters and NfL
- To explore the efficacy of Lu AF82422 for up to 72 weeks of treatment on clinical scales and biomarkers
- To collect patient experience with impaired functions due to MSA to support the interpretation of change on the UMSARS (Exit Interview subset)
- To collect patient experience with study participation (Study Experience Interview subset)

All during the Double-blind Period (DBP).

• To explore the effect of long-term treatment with Lu AF82422 during the open-label extension (OLE)

2 Study Design

- This is a phase II, interventional, randomized, double-blind, parallel-group, placebocontrolled, multi-centre study of the efficacy (slowing disease progression), safety, and tolerability of Lu AF82422 in patients with MSA. The efficacy of Lu AF82422 is assessed using the UMSARS TS; supportive assessments include evaluation of function, global impression of severity of illness, autonomic symptoms, disability, health-related quality of life, biofluid biomarkers, and imaging.
- The target population for this study is patients with possible or probable MSA, as defined by the 2008 Gilman diagnostic criteria. The study will recruit patients with evidence of parkinsonism (MSA-P) and/or cerebellar syndrome (MSA-C). Patients will be allowed stable treatment for managing their symptoms of MSA during the study.
- The patients [N=60] will be randomized to Lu AF82422 CCI or placebo (2:1) via a centralized randomization system (Interactive Response Technology [IRT]). Two strata variables will be applied to ensure a balanced treatment allocation of Lu AF82422 and placebo:CCI and Region (US/Japan, with a maximum of 25% of patients from Japan).
 - maximum of 25% of patients from Japan).
- The study duration from the Screening Visit to the Safety follow-up Visit is between 70 to 94 weeks for patients not entering the optional OLE period and between 118 to 142 weeks for patients continuing in the OLE. The study includes the following periods:
 - Screening period (4 weeks)
 - Randomization period (2 weeks)
 - Double-blind treatment period (48 weeks up to 72 weeks)
 - Optional OLE treatment period (48 weeks)
 - Safety Follow-up Period (20 weeks; will take place after last investigational medicinal product [IMP] administration)

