- The individual double-blind period will vary from 48 weeks up to 72 weeks. Once the last patient will reach Week 48, this visit will be the EoTDBP Visit for that patient. Patients who have not completed the visit at Week 72 at the time of Last Patient reaches EoT will have their next visit converted to an DBP EoT Visit with assessments as listed for Visit 24, according to study procedures and assessments (Appendix IV). During the double-blind treatment period, patients will attend IMP Visits to follow a dosing schedule with either Lu AF82422 or placebo every four weeks (Q4W).
- Patients who enter the OLE will receive the first open-label dose (Visit 1E) at the same day as the EoTDBP or as soon as possible thereafter, but not later than 5 months after EoT Visit of the DBP and will be enrolled to OLE no later than end of Q1 2024.
- After the DBP EoT/ End of Open-Label Treatment/Withdrawal Visit, patients will be scheduled for a Safety Follow-up Visit 20 weeks after last IMP dose.
- An independent Data Monitoring Committee (iDMC) will regularly monitor the patients' safety and tolerability data according to the Data Monitoring Committee (DMC) Charter.

An overview of the study is presented in Panel 1.

Panel 1 Study Design

1. Variable treatment period of minimum 48 weeks up to 72 weeks of treatment. Patients who have not completed Week 72 Visit at the time Last Patient reaches Week 48, will be scheduled for the EoT DBP Visit 4 weeks after latest dose of IMP

2. Patients who do not continue in the optional Open-Label Extension will enter the Safety Follow-up Period after the EoT DBP Visit

DBP = Double-Blind Period; EoT = End of Treatment; SoC = Standard of Care; Q4W = every 4 weeks

3 Definitions

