24.2 Assigning Data to Visits

Invalid assessments will be assigned AVISTN = 888. If the date of last dose is missing, assessments will be considered valid. If multiple assessments are taken the same day, only the last assessment will be valid. Invalid assessments will not be considered in descriptive statistics or statistical analyses but will be included in listings of safety variables.

Assessments at *unscheduled and withdrawal visits* will be assigned to a target day (AWTARGET) based on days after baseline visit, and to an analysis week (AVISTN = AWTARGET/7). Assessments falling outside a defined visit window will be evaluated and will be deemed invalid (AVISTN = 888) for that specific windowing approach in case no obvious week can be identified.

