ADA = Anti-Drug Antibody; AE = adverse event; ASL = arterial spin label; BL = baseline; CGI-S = Clinical Global Impression – Severity of Illness; CSF = cerebrospinal fluid; C-SSRS = Columbia-Suicide Severity Rating Scale; COMPASS = Composite Autonomic System Score; DNA = deoxyribonucleic acid; DTI = diffusion-tensor imaging; ECG = electrocardiogram; EoT = End-of-Treatment; EQ-5D-5L = Euroqol 5 Dimensions-5 Levels; IMP = investigational medicinal product; IRT = Interactive Response Technology; MoCA = Montreal Cognitive Assessment; MSA-C = Multiple System Atrophy with predominant cerebellar features; MSA-P = Multiple System Atrophy with predominant parkinsonism; MRI = magnetic resonance imaging; NfL = Neurofilament Light chain; OGI-S = Observer-rated Global Impression-Severity of Illness; PGI-S = Patient Global Impression-Severity of Illness; SAE = serious adverse event; SE-ADL = Schwab & England Activities of Daily Living; SFU = Safety Follow-up of DBP; SCR = screening; T-tau = total tau; UMSARS = Unified Multiple System Atrophy Rating Scale; vMRI = volumetric magnetic resonance imaging

a. When the last patient randomized reaches Visit 18/Week 48, the remaining patients in the double-blind treatment period will have their next scheduled visit converted to an EoT Visit (assessments as listed for Visit 24, no IMP administration).

b. Patients who withdraw, except for those who withdraw their consent, will be asked to attend a Withdrawal Visit as soon as possible.

c. The Safety Follow-up Visit will take place 20 weeks after last IMP administration. This will apply only to patients who do not enter the OLE or if timing of the safety FU will be before their first visit in the OLE.

Study 18331A - Statistical Analysis Plan

d. All assessments may be completed over a maximum of 2 consecutive days (except for MRI, see footnote w); if so, the first day is considered the "visit" day according to the schedule and at IMP Visits, IMP must be registered in IRT and administered on the second day. The Screening Visit can be performed over 2 days during the first week of the Screening Period.

e. If the date of a visit does not conform to the schedule, subsequent visits should be planned to maintain the visit schedule relative to screening for Visit 2 and Visit 3 and relative to baseline for visits after baseline.

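### SAP Panel 18 fixes the double-blind follow-up sampling window at Week 88, which at nominal timing fits only patients treated for 72 weeks

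*SAP*

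**What the plan says.** SAP section 24.2.3, Panel 18, sets the visit windows for blood sampling of drug concentration, safety laboratory tests, alpha-synuclein and ADA. Its lead-in adds the safety follow-up visit to the windowing. The double-blind follow-up row, "V25 (planned sampling SFU Visit", has nominal Week 88, Day 616, narrow window 609-623 and broad window 595-630. The row before it, "V24 (planned sampling EoTDBP/WD Visit", ends at Day 518 in both versions. The panel's footnote says the narrow windows run continuously so that assessments are not invalidated.

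The visit is timed differently. Protocol Panel 2, footnote c, repeated in SAP Appendix IV, says: "The Safety Follow-up Visit will take place 20 weeks after last IMP administration". SAP section 2 states: "The individual double-blind period will vary from 48 weeks up to 72 weeks". Under SAP Panel 1, note 1, patients who have not completed Week 72 when the last patient reaches Week 48 "will be scheduled for the EoT DBP Visit 4 weeks after latest dose of IMP". The flow chart describes the converted end-of-treatment visit as "assessments as listed for Visit 24, no IMP administration".

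For records that miss a window, SAP section 24.2 says: "Assessments falling outside a defined visit window will be evaluated and will be deemed invalid". The sentence goes on to limit this to the windowing approach concerned and to cases where no obvious week can be found. Invalid records (code 888) leave the descriptive statistics and analyses but stay in the safety listings.

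**The concern.** The window counts from baseline, while the visit counts from the last dose. The two agree only when the last dose falls at Week 68. Treatment length varies by design in this trial, so the mismatch would affect regular completers as well as occasional withdrawals.

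At stake is whether off-drug samples are summarised as follow-up. Plasma drug concentration during treatment and follow-up is a secondary endpoint, and plasma free and total alpha-synuclein over the same span is exploratory. The protocol gives a half-life of about 28 to 30 days. Assuming mono-exponential decline, 16 weeks (112 days) after end of treatment the concentration is 2^(-112/28) = 6% to 2^(-112/30) = 8% of that patient's end-of-treatment level. Such values, averaged under a Week 60 to Week 72 label, would distort the late exposure and target-engagement profiles. Samples coded 888 would drop out of the follow-up summary.

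**Working it through.** **Inputs.** Follow-up is 20 weeks after the last dose (Protocol Panel 2, footnote c). End of treatment (EoT) is 4 weeks after the last dose, with no dose at that visit (SAP Panel 1, note 1; SAP Appendix IV, Table 1, footnote a). EoT falls at Weeks 48 to 72 in 4-week steps. Screening is 6 weeks before baseline. Windows are from Panel 18.

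**Reproducing the plan's own figures.** SAP section 2 says the study duration "is between 70 to 94 weeks for patients not entering the optional OLE period". Shortest: 6 + 44 + 20 = 70 weeks. Longest: 6 + 68 + 20 = 94 weeks. Both ends agree, so the documents themselves place follow-up between Week 64 and Week 88. The Panel 18 anchor is the upper end only: (68 + 20) x 7 = Day 616, and 616 +/- 7 = 609-623.

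**Assignment for completers.** Follow-up day = (EoT week - 4 + 20) x 7, looked up in Panel 18:

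| EoT week | Last dose week | Follow-up week | Day | Narrow window | Broad window |
|---|---|---|---|---|---|
| 48 | 44 | 64 | 448 | V22 (435-462) | V21 (379-462) |
| 52 | 48 | 68 | 476 | V23 (463-490) | V24 (463-518) |
| 56 | 52 | 72 | 504 | V24 (491-518) | V24 (463-518) |
| 60 | 56 | 76 | 532 | none | none |
| 64 | 60 | 80 | 560 | none | none |
| 68 | 64 | 84 | 588 | none | none |
| 72 | 68 | 88 | 616 | V25 (609-623) | V25 (595-630) |

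The uncovered days are 519-608 (narrow) and 519-594 (broad), so the footnote's claim of continuity fails between V24 and V25.

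**Visit tolerance.** Moving each visit by the scheduled +/-7 days changes one entry. A 68-week patient seen at Day 588 + 7 = 595 just enters the broad V25 window, but not the narrow one.

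**Early withdrawals.** A last dose at Weeks 0 to 40 gives follow-up at Weeks 20 to 60 (Days 140 to 420), always inside an on-treatment window. For example, a last dose at Week 28 gives (28 + 20) x 7 = Day 336, which is V18, Week 48.

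**Does the record-priority rule repair it?** SAP section 24.2.1 chooses between two records of one patient in the same analysis week. For EoT at Weeks 48, 52 or 56, the patient has no planned on-treatment sample in the window where the follow-up sample lands. There is then nothing to displace it.

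**Open-label extension.** The SFU-E row is Week 64E, Day 448 (434-462). This fits a last dose at Week 44E: (44 + 20) x 7 = 448. A patient whose last dose is at Week 24E is due on (24 + 20) x 7 = Day 308, inside the V12E narrow window (295-322) and the V13E broad window (295-350).

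**The case against.** The strongest reply is that the misassignment is inferred. The sentence in SAP section 24.2 that assigns records by days after baseline names unscheduled and withdrawal visits, whereas V25 is a scheduled, numbered visit. Protocol Panel 2 also prints Week 88 for V25 while its footnote times the visit from the last dose, so Week 88 may be only a nominal label. If records taken at V25 keep that label, no off-drug sample enters a treatment window. This is a fair reading of intent, but the SAP does not state it. Panel 18 gives V25 a day window like every other row, and no rule exempts it.

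Three stronger readings are tempting, and the documents do not support them.

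- **That Week 60-68 samples are automatically invalid.** Out-of-window records are evaluated first and coded 888 only if no obvious week is found. A sample recorded at V25 could reasonably be judged to have one.
- **That about 75% of follow-up samples are affected.** This is the complement of the sample-size assumption that about 25% of patients contribute 72 weeks of data. That share is of all patients, before the 20% drop-out allowance. The double-blind follow-up visit applies only to patients who do not enter the extension or whose visit falls before entry, and the documents give no duration mix for them.
- **That ADA and safety findings are lost.** SAP section 18 defines ADA status per subject over treatment and follow-up, and all immunogenicity data are listed. SAP section 16.2 uses all available assessments in each period for PCS values. Invalid safety values remain in listings. Population PK has its own plan, and nothing shows that it uses these windows.

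**Conclusion.** Panel 18's follow-up window is wrong as written. At nominal timing it fits one of the seven possible end-of-treatment weeks. Three (48, 52, 56) send the follow-up sample to a treatment window, and three (60, 64, 68) send it to none. Earlier withdrawals also land in treatment windows.

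This rests on two assumptions: visits occur at nominal timing, and the windows are applied to V25 as printed. The harm is confined mainly to late by-visit summaries of plasma drug concentration, alpha-synuclein and safety laboratory values, and to an incomplete follow-up summary. The primary UMSARS analysis does not use Panel 18. Per-subject ADA status and PCS evaluation are largely unaffected; an ADA sample finally coded 888 is the possible exception.

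The number of patients affected cannot be derived from the documents. The SFU-E window has the same defect on a smaller scale: within the SAP's 48-week extension, completers fit and only early leavers miss.

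**What to change.** In Panel 18, replace the fixed V25 and SFU-E rows with a window on day of last dose + 140. The scheduled tolerance of +/-7 days is one option, and a wider one would also work. Add one sentence: samples recorded at the SFU or SFU-E visit are assigned to that visit before the treatment windows are applied.

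With +/-7 days the completer windows become 441-455, 469-483, 497-511, 525-539, 553-567, 581-595 and 609-623 for EoT at Weeks 48, 52, 56, 60, 64, 68 and 72. Each follow-up sample then maps to follow-up, and the 72-week patient keeps the current narrow window. Anchoring on the last dose would also cover the current protocol's extension, where a last dose at Week 92E puts SFU-E at Week 112E.

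The cost is two table rows and one sentence in the SAP. No new data are needed, and no efficacy analysis changes.
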